In Aim 1, we interviewed severely obese Veterans and the providers that treat them to identify and understand the facilitators and barriers that affect treatment decisions. An analysis of the transcripts of these interviews led us to the conclusion that patient knowledge was a major barrier to treatment. Subsequently, our team worked to develop an educational video that could be used to teach Veterans what their treatment options were within the VA. This video was presented to four patient stakeholder panels and multiple providers for feedback. We updated the video iteratively according to the feedback we received. The result was an 18 minute educational video that will be presented to Veterans in this pilot study.

The VA is well positioned to lead national improvements in bariatric surgery care. With implementation of the "MOVE!" program in every VA medical center for more than five years, obesity screening has occurred for more than 95% of Veterans.^{5,6} This high rate of obesity screening via a centralized program for weight management is unique and represents an opportunity for policy and practice refinements to have a large impact.

Summary of Significance: This study addresses an important public health issue: pursuing effective treatment options for more than 600,000 severely obese Veterans. Currently, less than 1% of severely obese patients pursue bariatric surgery, despite its known effectiveness in comorbidity resolution and improved quality of life. Very little published data exists to explain why so few Veterans pursue this treatment option. The knowledge generated in this study will provide information on whether an educational video designed to enhance shared decision-making is feasible and acceptable to Veterans

II. RESEARCH DESIGN, METHODS, and DATA ANALYSIS

[figure not shown]
Study Aim: Pilot-test an educational video that aligns patient preferences with treatment options to optimize the care that severely obese Veterans receive.

Purpose and goals: We will assess acceptability and feasibility of implementing the educational video and seek evidence of a signal as to whether patient knowledge and decision-making are improved with use of an educational video. Using ORBIT⁷ Figure 1: ORBIT Model for developing behavioral treatments for chronic diseases

ORBIT⁷ as our framework (Figure 1), this is considered phase IIb preliminary testing of our intervention.

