1. Participants will then be randomized to the intervention or usual care arm with probability equal to 1/2 (i.e., 1:1 randomization) using a computerized random number generator in blocks (size < 10; all study personnel except the statisticians are blinded to block size). The randomization assignment will be revealed to the patient by the un-blinded researcher. If the patient is randomized to the intervention, he/she will be shown the educational video the same day. The educational video is an 18 minute video that describes the risks of obesity and explores the three weight management options available to patients with severe obesity (BMI ≥ 35) in the VA. The video explains the weight loss treatments the VA offers, how to access them, what eligibility criteria patients might have to meet to obtain them, and describes the typical health outcomes for each treatment. Patients will also hear stories from Veterans who went through one particular treatment option. Patients randomized to usual care will not be shown the educational video.
2. Patients will be asked to complete a post-assessment within 7-14 days of their MOVE! visit. Patients randomized to the intervention arm will also be asked to participate in a 10-minute interview in addition to the post-intervention assessment. The post-intervention assessment and interview (intervention arm only) will be scheduled prior the patient's MOVE! visit. This post-assessment will be completed over the phone approximately 7-14 days after their MOVE! visit. Veterans may be reminded of this call via text message, phone call, or email prior to their appointment. They may also opt out of receiving a reminder. All email communications will come from a researcher's VA email account. Following their post-assessment call (and regardless of whether they complete their post-assessment call), a monetary incentive will be provided to participants for their time (\$50).

Measures: Demographic data will be collected at baseline, prior to learning of randomization assignment. Signal of effect (patient outcomes), intervention fidelity, acceptability of the intervention, and feasibility measure will be collected during the pre- and/or post-intervention period as outlined in **Table 1**.

Table 1: Measures for Pilot Testing (Pre and Post-Intervention)

[figure not shown]
Measure	Pre	Post	Reliability	Validity	Group
Patient Demographics	X		N/A	N/A	Both
Patient Outcomes					

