Primary patient outcome: Behavioral intentions in pursuing any of the 3 treatment options in the VA		X			Both
Secondary patient outcome #1: Preparation for Decision-making Scale (10 Qs) ³		X	$\alpha=0.92-0.96^3$	Scores correlated with the informed ($r=0.21; p<.01$) and support ($r=0.13, p=.01$) DCS subscales ³	Both
Secondary patient outcome #2: Patient knowledge and attitudes (Informed Choice; 12 Qs) ⁴		X	$\alpha=.82^4$	Mean knowledge score correlated with responses to open-ended questions designed to elicit their understanding of the test ⁴	Both
Secondary patient outcome #3: Self-efficacy measure		X	N/A	N/A	Both
Secondary patient outcomes #4: Process and outcome measures, including patient checked the box for bariatric surgery or requested to go down the bariatric pathway or patient checked the box for MOVE! visits or requested to go down the MOVE! pathway; attending MOVE! bariatric visit, info session, bariatric referral, bariatric visit, bariatric surgery, bariatric outcomes		X	N/A	N/A	Both
Acceptability					
Acceptability to patients: Qualitative interview		X	N/A	N/A	Intervention only
Feasibility					
Recruitment and Attendance Rates	X	X	N/A	N/A	Both
ICC=Intra-class correlation coefficient; IRA=inter-rater agreement					

1. Patient demographics: Baseline patient demographics including age, gender, sex, race, BMI, comorbidities, pregnancy status (if female), and contact information will be obtained from the electronic health record.

2. Primary patient outcome - Behavioral intentions: Behavioral intentions to pursue bariatric surgery or treatment in the MOVE! program will be assessed separately with five semantic differential items ranging from 1 to 7 (unlikely to likely; not possible to certain) following the methods of Azjen.⁸

3. Secondary patient outcome - Preparation for decision-making: Patients will complete the Preparation for Decision-making questionnaire which consists of 10-items that assesses the patient's opinion about the effect of the educational video had on his/her decision (e.g. "Did this educational material help you think about which pros and cons are most important").⁹

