6. Process measures: We will record whether patients “checked” the bariatric surgery MOVE! visit box in their MOVE! intake form. We will record whether patients attended a MOVE! bariatric visit, attended a bariatric surgery info session, received a bariatric referral, attended a bariatric surgery visit, underwent bariatric surgery, and lost weight after bariatric surgery. We will also track the number of MOVE! visits the patient has as well as any change in weight. These variables will be obtained from a data pull from the Corporate Data Warehouse (VA Database) at the end of the study.

7. Acceptability to patients (patient interviews): Acceptability of the educational video to patients will be assessed during a 10 minute semi-structured interview that will be conducted during the post-intervention assessment phone call for patients in the intervention arm. The patient will be asked several questions about use of the educational video, including the extent to which the amount of information presented was appropriate, clear, and in hindsight, the ideal timing of administration of the educational video. Patients who complete the intervention via VVC will be asked questions about their experience using the VVC system.

8. Feasibility of recruitment: Feasibility will be assessed by measuring recruitment and retention rates. The recruitment rate is defined by the number of Veterans who indicate, during a recruitment phone call, that they will participate divided by the number reached. Reasons for declining will be captured and analyzed for future study design optimization. The retention rate is defined as the number who watch the video and complete all assessments, divided by the number scheduled. A priori feasibility targets are $\geq 60\%$ recruitment and $\geq 80\%$ retention.

Data analysis and sample size: Descriptive statistics will be used to characterize patient demographics, secondary patient outcomes, and acceptability by group. Analysis of the primary outcome will treat pre- and post-intervention outcomes as two repeated measures on each subject. The regression model will include a post-visit indicator, an intervention group indicator, and an interaction between the two, the coefficient of which will be the parameter of interest capturing the intervention effect. To account for the repeated measures within patient, the model will include a random patient effect.

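### The Preparation for Decision-making scale is defined by the video and given to both arms, but usual-care patients see no video and are assigned nothing else to rate

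*Combined protocol and SAP*

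**What the plan says.** Five places in the combined protocol and SAP bear on this point.

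- **Measures, item 3** describes the scale as capturing the patient's "opinion about the effect of the educational video had on his/her decision". The only item shown is "Did this educational material help you think about which pros and cons are most important".
- **Table 1**, in the row beginning "Secondary patient outcome #1: Preparation for Decision-making Scale (10 Qs", marks the scale for collection at Post only, with Group entry *Both*.
- **Study Procedures, step 1** states: "Patients randomized to usual care will not be shown the educational video".
- **Purpose and goals** says that the study will "seek evidence of a signal as to whether patient knowledge and decision-making are improved with use of an educational video".
- **Data analysis and sample size** states: "Descriptive statistics will be used to characterize patient demographics, secondary patient outcomes, and acceptability by group".

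Table 1 does restrict one other measure about the video. The row "Acceptability to patients: Qualitative interview" has Group entry *Intervention only*.

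**The concern.** A scale that asks how well something prepared a patient for a decision needs an object that the patient has met. Here the stated object is the video, and by design one arm never meets it. A usual-care patient asked these ten questions might rate the MOVE! visit, rate nothing and choose low or middle answers, or call the questions not applicable. The plan does not say which of these is intended or how such answers would be scored.

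A difference between arms could then reflect whether patients had anything to rate, rather than how well prepared they were to decide. The scale is collected only after the intervention, so there is no within-patient change to fall back on. It is the first-listed secondary patient outcome, and its subject is part of the signal that the pilot is looking for. The pilot is also meant to supply preliminary variability data for a later efficacy trial, and usual-care scores with no defined object would serve that purpose poorly.

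**Working it through.** The plan gives no figure to reproduce, and the point turns on definitions. The check sets the relevant parts side by side.

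1. **What is rated.** Item 3 names the educational video. The example item speaks of educational material without naming a source, but it is offered as an illustration of a scale that the same sentence ties to the video.

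2. **Who rates it.** Table 1 says *Both*.

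3. **Who has seen it.** Study Procedures, step 1, shows the video to the intervention arm only.

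4. **Whether usual care is given another object.** The recruitment text, Study Procedures, Measures items 1 to 8, Table 1 and the analysis section contain no statement that usual-care patients should rate the MOVE! visit, its handouts or anything else. They give no adapted wording and no rule for not-applicable answers.

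5. **Whether *Both* could be a blanket entry.** It is not, because the acceptability interview is marked *Intervention only*. The remaining patient-reported outcomes carry *Both* without difficulty, since they ask about treatments: intentions to pursue bariatric surgery or MOVE! (item 2), knowledge and attitudes (item 4) and self-efficacy (item 5). The process measures (item 6) are recorded data. Only this scale, as described, presupposes that the patient saw the video.

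6. **Whether the analysis text resolves it.** It does not. Secondary patient outcomes are to be described by group. The same sentence applies that phrase to acceptability, which is collected in one arm only, so it is too loose to supply the missing object.

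7. **How many patients are affected.** The inputs are a recruitment maximum of 40 (Data analysis and sample size) and 1:1 allocation (Study Procedures, step 1). The usual-care arm is 40 × 1/2 = 20, so about 20 patients at full recruitment, on 1 of the 4 secondary patient outcomes in Table 1.

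The size or direction of any distortion in the scores cannot be worked out. The documents give no expected scores, no standard deviation and no rate of unanswered items for this scale.

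**The case against.** The best defence is that usual-care patients do have something to rate. All participants are recruited through an in-person MOVE! visit, and the Background describes MOVE! as a place where patients learn about losing weight. The post-assessment is timed from that visit in both arms, and the example item can be answered about MOVE! content. On this view item 3 is one loosely worded sentence. Because the authors wrote *Intervention only* where they meant it, *Both* may be deliberate, with a suitable stem in a questionnaire that the reader cannot see.

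Part of this stands. An adapted form may exist, so the point is limited to what the plan says, and it would be wrong to conclude that the scale cannot be answered in usual care. But a possible object is not an assigned one, and the plan's own definition names the video. Intervention patients attend the MOVE! visit too. If usual care rates the visit while the intervention arm rates the video, the two arms are scoring different things, and the by-group summary still does not compare like with like.

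It is also fair to say that the stakes are modest. The summary is descriptive, and the plan states that the pilot does not evaluate statistical significance. That limits the weight of the point, but the conflict between the stated rules remains.

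**Conclusion.** The point holds. As written, secondary patient outcome #1 has no defined object for about 20 of up to 40 patients, and its by-group summary cannot be read as a signal that the video improves decision-making. This assumes full recruitment, 1:1 allocation and no usual-care form beyond the documents. The primary outcome, the other three secondary patient outcomes and the sample size are unaffected.

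Three stronger readings might be inferred, and the documents do not support them.

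- **That the scale will exaggerate the video's effect.** Neither the direction nor the size of any distortion can be derived.
- **That usual-care patients who skip the scale will pull retention below its 80% target.** Item 8 states: "The retention rate is defined as the number who watch the video and complete all assessments, divided by the number scheduled". Read literally, the requirement to watch the video already keeps every usual-care patient out of the numerator, so skipping this scale changes nothing. The documents also give no rate of skipping.
- **That a neutral stem would necessarily depart from the validated wording.** Only one example item is shown, and it is already generic, so this cannot be settled from the documents.

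**What to change.** Choose one of two options.

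**(a) Intervention arm only.** Change the Table 1 Group entry for this scale to *Intervention only*, say the same in item 3, and state in the analysis section that the scale is reported as a single-arm description. The between-arm decision-making signal then rests on informed choice (secondary patient outcome #2). The cost is the loss of a between-arm summary of this scale.

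**(b) Both arms, one object.** Use the same neutral stem in both arms, asking about the weight-management information received at or around the MOVE! visit, and reword item 3 to match. The stem must be identical in the two arms, so that the contrast is between information with the video and information without it. Add a note to Table 1 that, if this stem differs from the validated wording, the cited reliability (alpha 0.92 to 0.96) and validity (r = 0.21 and 0.13) figures may not apply. The cost is a possible change to the instrument's wording.

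If a suitable usual-care form already exists, describe it in item 3 and Table 1, and confirm that both arms rate the same object.

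Neither option needs more patients, visits or calls. The plan identifies patients from MOVE! visits beginning in May 2019, and the document is dated 02/12/2020, so enrolment may have started; the documents do not say. If responses have already been collected under video-specific wording, those from usual care should not be used as a comparator.

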CPRS. Veterans will qualify as severely obese if their BMI is ≥ 35 within the last six months of being referred to MOVE!. Given that more than 300 severely obese patients were referred to the Madison VA MOVE! program annually, meeting our recruitment goal (up to 40) will require participation of 20% of severely obese patients over the course of a year.

Research staff will use CPRS, outpatient MOVE! appointment requests from CDW, and/or automated reports to identify Veterans with severe obesity between the ages of 18 and 75 who are scheduled to attend an in-person MOVE! visit at the Madison VA. Research staff will review upcoming MOVE! clinic appointments for eligible patients. Subsequent visits and subject eligibility will be assessed weekly. Eligible patients who have a MOVE! visit following 7 or more days of newly reviewed upcoming clinic visits will be sent a recruitment letter and/or email ahead of their visit with a brief explanation of the study inviting them to participate. The letter and/or email will state that the research team may call and/or email them up to 3 times over the next 3 months. Patients who agree to participate in the study over the phone, and who qualify for the study will be asked to arrive at their MOVE! visit 50 minutes early to go over the consent process and be placed into intervention/usual care arms.

Study Procedures:

Our researcher will meet each patient who has been recruited in a private room to go over the consent process. If patients are interested in participating in the study, they will be asked to sign a written informed consent to participate in the study as well as a HIPAA form to collect process measures. They will also complete a demographic survey.

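### The recruitment rate compared with the 60% target counts phone agreement among Veterans reached, so losses at attendance, consent and randomisation do not enter it

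*Combined protocol and SAP*

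**What the plan says.** All references are to section II of the combined protocol and SAP.

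- **Measures, item 8 (Feasibility of recruitment).** The recruitment rate is "the number of Veterans who indicate, during a recruitment phone call, that they will participate divided by the number reached". For retention: "The retention rate is defined as the number who watch the video and complete all assessments, divided by the number scheduled". The thresholds follow: "A priori feasibility targets are $\geq 60\%$ recruitment and $\geq 80\%$ retention". Reasons for declining are to be captured.
- **Study population and recruitment.** After the call, "Patients who agree to participate in the study over the phone, and who qualify for the study will be asked to arrive" early for their MOVE! visit. The purpose of the 50 minutes is the consent process and allocation to an arm.
- **Study Procedures.** Consent is taken in person and is conditional: "If patients are interested in participating in the study, they will be asked to sign a written informed consent". A HIPAA form and a demographic survey are also completed. Then, under step 1, "Participants will then be randomized to the intervention or usual care arm with probability equal to 1/2". Usual-care patients are not shown the video.
- **Table 1.** The feasibility row is labelled "Recruitment and Attendance Rates" and applies to both groups. Item 8 neither defines an attendance rate nor sets a target for one.

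**The concern.** Feasibility is one of the pilot's stated purposes, the sample size is justified partly on it, and the results are meant to support a later, adequately powered trial. That trial needs to know how many contacted Veterans end up randomised.

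The rate compared with 60% stops at a verbal yes. The plan itself expects that some who say yes may go no further, because consent depends on continued interest at the visit. Coming in 50 minutes early is a real demand, and its effect on enrolment is something a pilot should measure. If the loss after the call is sizeable, the target can be met and recruitment reported as feasible while the randomised yield is well below 60%.

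**Working it through.** The 60% is a chosen threshold with no derivation, and the plan has no power calculation, so there is no figure of the plan's own to reproduce. The check is to follow the definition through the later steps.

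**Inputs**
- Phone agreement/reached: 60%, exactly at target (item 8).
- Maximum sample: 40 (Data analysis and sample size).
- c, the share of those agreeing by phone who attend, consent and are randomised: not in the documents. Assumed to be 0.7 to 0.9, with 1.0 as the no-loss case.

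**Formulas**
- Randomised/reached = 0.60 × c
- Phone agreement needed for 60% of those reached to be randomised = 0.60/c
- Veterans to be reached to randomise 40 at 60% phone agreement = 40/(0.60 × c), rounded up

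| c | Randomised/reached | Phone agreement needed | Reached for 40 randomised |
|---|---|---|---|
| 1.0 | 60% | 60.0% | 67 |
| 0.9 | 54% | 66.7% | 75 |
| 0.8 | 48% | 75.0% | 84 |
| 0.7 | 42% | 85.7% | 96 |

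The recruitment target is met in every row, because c does not appear in the definition. The ratios use all Veterans reached. If some prove ineligible, randomised/eligible reached would be somewhat higher.

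**Does the 80% retention target pick up the same losses?** That depends on what scheduled means.

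1. *Booked for the visit during the phone call.* Suppose everyone who agrees is booked, and the video requirement is waived for usual care. Meeting both targets then implies randomised/reached of at least 0.60 × 0.80 = 48%. No-shows and refusals of consent count against retention on this reading.
2. *Booked for the post-assessment call after consent.* Losses between the phone yes and consent then appear in neither rate. Study Procedures, step 2, says this call is arranged before the MOVE! visit, which could be before or after consent.
3. *Numerator taken literally over both arms.* Only intervention patients watch the video. With 1:1 allocation of 40, at most about 20/40 = 50% could qualify, so 80% is out of reach.
4. *Intervention arm only.* Veterans booked by phone have no arm yet, so the denominator has to start at randomisation, and earlier losses are again outside it.

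Only the first reading gives a bound on the randomised yield, and it needs two assumptions that the plan does not state.

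**The case against.** The strongest reply is that item 8 assesses feasibility on recruitment and retention together. On the first reading above, a Veteran who agrees and does not turn up counts against the 80%, so passing both targets guarantees at least 48% randomised/reached. This stands as a partial safeguard. It is not a reliable one, because the plan does not say which booking it means and the numerator does not fit the usual care arm.

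Second, acceptance among those contacted is explicit and reproducible, and it contradicts nothing else in the document. That stands too: the weakness lies in what the target measures. It is not an error or an inconsistency.

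Third, eligibility is screened from the chart before letters go out, and qualifying is a condition for being asked to come in early. It is therefore probably a small part of the later loss; attendance and written consent matter more.

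Fourth, applying the same 60% to a stricter ratio would raise the bar without justification. At c = 0.8 it would require 75% phone agreement. This stands, and the fix allows for it.

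Two stronger readings are tempting and not supported:
- A reader might infer that feasibility could be declared with nobody randomised. At c = 0 the recruitment target alone would indeed be met, but the retention target needs people who watched the video and completed the assessments.
- A reader might set the 40 Veterans against the more than 300 annual MOVE! referrals and treat the result as the expected yield. The 40 is a ceiling, and the referrals are neither Veterans invited nor Veterans reached.

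**Conclusion.** The point holds for the recruitment rate and its 60% target. As defined, that rate cannot show losses between the phone call and randomisation, and the retention and attendance measures as written do not reliably fill the gap. At exactly 60% phone agreement, randomised/reached is 42% to 54% if 70% to 90% of those agreeing are randomised. This range rests wholly on the assumed conversion; the documents give no figure, and with no loss the rate would be the full 60%. The 60% is a benchmark for comparison: no test or confidence interval is attached to it. The change should be made before the feasibility conclusion is drawn, because this is a main question of the pilot and the change is small.

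**What to change.** In item 8:

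1. Keep phone agreement/reached as an intermediate measure, and label it acceptance.
2. Add randomised/eligible Veterans reached as the recruitment rate on which the feasibility conclusion rests. Set its target before the data are seen, either 60% or another value with a stated reason.
3. Report the flow: invited, reached, agreed, attended, consented, randomised. This also shows Veterans who were invited but never reached, who are outside both ratios.
4. State which step of that flow scheduled refers to in the retention rate.

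**Cost.** Patient procedures do not change. The reported recruitment rate will be less favourable and its target may be missed. Staff must log a count at each step: section IV says the identifier linkage lets staff track enrolment, but it does not say that every one of these counts is recorded.

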We aim to sequentially recruit up to 40 severely obese Veterans. Patients will be randomized to one of the two groups. Based on prior experiences from our co-investigator team and the literature on usability testing¹⁷ this sample size will be sufficient to assess feasibility and acceptability and seek evidence of signal regarding intervention effects. A power calculation will not be performed given that we are not evaluating statistical significance of the intervention at this point; rather, we are seeking an indication of clinically significant change, preliminary data on within- and between-subject variability in these measures, and evaluation of the feasibility of the study (cite A). Quantitative data will be analyzed using SAS version 9.3 (or higher) (SAS Institute, Cary, NC).

Data analysis approach: The digital audio recordings from all patient interviews will be transcribed by a transcriptionist who will be supported with CDA research funds. We will use a directed approach to content analysis,¹⁸ developing codes (descriptive labels) based on predetermined categories, such as those derived from interview questions. Any text that cannot be categorized with the pre-determined scheme will also be identified and categorized. Drs. [name] and [name] and our Researcher will analyze the first five patient transcripts. After analysis of the first patient transcripts, they will convene to adjudicate each coded phrase or idea. This procedure will be repeated for each subsequent transcript using the technique of constant comparison, ultimately developing a taxonomy of consensus codes.¹⁹ Each transcript will then be re-coded according to this coding scheme. Then higher-level coding will be conducted to identify themes and trends in the data to consolidate feedback for refinement of the analysis. The theme matrix technique²⁰ will be used to identify patterns in the data based on patient characteristics. Data will be managed and categorized using NVivo.

III. Data and Safety Monitoring Plan

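### The plan seeks a signal on patient knowledge and decision-making, but pre-specifies no between-arm difference or interval for knowledge or informed choice

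*Combined protocol and SAP*

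**What the plan says.** All references are to section II of the combined protocol and SAP.

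- **Purpose and goals.** Besides acceptability and feasibility, the study will "seek evidence of a signal as to whether patient knowledge and decision-making are improved with use of an educational video".
- **Table 1.** Knowledge and attitudes (informed choice) is secondary outcome #2, and the Preparation for Decision-making Scale is #1. Both are collected in both arms and marked under Post only.
- **Data analysis and sample size.** For these outcomes the plan is: "Descriptive statistics will be used to characterize patient demographics, secondary patient outcomes, and acceptability by group". The primary outcome, behavioral intentions, gets a model: "The regression model will include a post-visit indicator, an intervention group indicator, and an interaction between the two", plus a random patient effect. The interaction coefficient is the intervention effect.
- **Same part, on size.** "We aim to sequentially recruit up to 40 severely obese Veterans". Also: "A power calculation will not be performed given that we are not evaluating statistical significance of the intervention at this point". The plan looks for change of clinical importance but attaches no number to it for any outcome. Numerical targets are set in advance only for recruitment (60%) and retention (80%).

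No confidence interval is mentioned anywhere in the document.

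**The concern.** Whether an outcome is improved by the video is a question about the difference between the randomized arms. For knowledge and informed choice the plan commits only to a summary of each arm. The reader would then compare two means or two proportions with no stated uncertainty for their difference.

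With at most about 20 patients per arm, moderate differences arise by chance often enough to matter. The results are meant to support a later efficacy trial. A chance difference on knowledge or informed choice could be reported there as the signal, with nothing beside it to show how imprecise it is.

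**Working it through.** The plan has no power or precision figure to reproduce, so the check asks how informative the between-arm contrast would be.

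**Inputs**
- Sample: up to 40, allocated 1:1, so n = 20 per arm at best (Data analysis and sample size; Study Procedures).
- With losses: 80% retention is the plan's target. 0.80 × 40 = 32, so n = 16 per arm if losses are equal (assumption).
- SD: none is given, so results are in SD units with a common SD (assumption).
- Threshold for a signal: none is given, so a range is shown (assumption).

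**Continuous outcome, such as the knowledge score**

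Standard error of the difference = √(2/n):
- n = 20: √(2/20) = 0.316 SD
- n = 16: √(2/16) = 0.354 SD

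95% half-width = t(0.975, 2n − 2) × SE:
- n = 20: 2.024 × 0.316 = 0.64 SD
- n = 16: 2.042 × 0.354 = 0.72 SD

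Chance that one outcome favours the video by at least d with no true effect = 1 − Φ(d/SE). This is one-directional, because the question is about improvement.

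| d (assumed) | n = 20 per arm | n = 16 per arm |
|---|---|---|
| 0.2 SD | 26% | 29% |
| 0.3 SD | 17% | 20% |
| 0.5 SD | 5.7% | 7.9% |
| 0.8 SD | 0.6% | 1.2% |

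For example, 0.3/0.316 = 0.949 gives 17%, and 0.5/0.354 = 1.414 gives 7.9%.

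**Binary outcome, informed choice**

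Assume the same true rate p in both arms, between 30% and 50% (the plan gives none). Half-width = 1.96 × √(2p(1 − p)/n):
- n = 20: 1.96 × √(0.42/20) = 28 points at p = 0.3; 1.96 × √(0.50/20) = 31 points at p = 0.5
- n = 16: 32 and 35 points

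By exact binomial calculation, a chance gain of at least 20 points for the video occurs in 11–13% of trials at 20 per arm and 9–11% at 16 per arm. The second range is lower only because of discreteness: with 16 per arm, 3/16 is 18.75 points, so the smallest qualifying gain is 4/16, or 25 points.

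**The case against.** The strongest reply is that this is a small pilot that openly declines significance testing. Descriptive reporting of secondary outcomes is a legitimate choice at this size, and that stands: the plan is not at fault for lacking a test or a power calculation. But an exploratory estimate with an interval is not a test, and the plan already intends an effect estimate for its primary outcome.

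A second reply is that the contrast is recoverable. These outcomes are post only, so n, mean and SD per arm, or counts, give the difference and its interval. That is true if those statistics are reported. The plan does not say which will be, and a quantity that a reader could work out is not a pre-specified analysis.

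A third reply is that decision-making does have a modelled contrast, since behavioral intention is the primary outcome and stands in for choice in the informed-choice measure. This stands in part. Intention is not knowledge, and informed choice combines knowledge, attitude and choice.

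Some stronger readings are tempting but not supported:

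- **That about a third of null trials would show a false signal.** The chance of a difference of at least 0.3 SD in either direction is 34% at 20 per arm and 40% at 16 per arm. Half of those trials favour usual care, which nobody would read as improvement.
- **That the pilot would leave the next trial without variability estimates.** By-group descriptive statistics normally supply the SDs or rates needed, and the plan names variability data as a goal.
- **That moving to the efficacy trial depends on these outcomes.** No such rule is stated, and acceptability and feasibility come first in the purpose.

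**Conclusion.** The point holds for knowledge and informed choice: the stated analysis does not give the plan's own randomized question an estimate with its uncertainty. For decision-making more broadly the gap is partial.

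The size is moderate. Chance differences of 0.3 SD in favour of the video are fairly common, those of 0.5 SD uncommon, and those of 0.8 SD rare. The intervals would be wide enough to include no effect at most of the differences likely to be discussed, and separate arm summaries do not display this.

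These figures assume a common SD, a normal approximation for the chance probabilities, and 16 to 20 analysed patients per arm. Because 40 is an upper limit, precision could be worse. The thresholds are illustrations, not the plan's. The trial's validity and its primary analysis are not in question, so this is a change that should be made rather than one the trial depends on.

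**What to change.** Add to the analysis paragraph, before unblinded data are summarised:

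- **Knowledge score:** between-arm mean difference with a 95% confidence interval.
- **Informed choice:** between-arm risk difference with a 95% confidence interval, using the classification in the informed-choice rubric.
- **Self-efficacy:** the same as for knowledge, if wanted. The purpose does not name it, so this is optional.
- **Labelling:** exploratory, with no significance claims.

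No baseline adjustment should be specified. The study design paragraph speaks of assessment before and after the video but defers to Table 1, which shows no pre-score for these outcomes.

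Preparation for Decision-making items that refer to the educational material should not be contrasted between arms. Usual care does not see the video, so an interval would not make that comparison interpretable.

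The cost is a few lines of SAS and one table, with no change to design, data collection or sample size. The downside is that the intervals will be wide and any reported signal will look less certain.
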